Identified risks for upadacitinib are summarized in the upadacitinib Investigator's Brochure⁸ and include: serious infections, opportunistic infections and tuberculosis (TB), and herpes zoster. Potential risks for upadacitinib include: malignancies, including lymphoma and non-melanoma skin cancer (NMSC), gastrointestinal (GI) perforations, major adverse cardiovascular events (MACE), hematologic changes (anemia, neutropenia, and lymphopenia), increased serum creatinine and renal dysfunction, hepatic events and increased hepatic transaminases, elevated creatine phosphokinase (CPK), embolic and thrombotic events (non-cardiac, non-central nervous system [CNS]), and fetal risks.

As of 15 December 2019, 171 healthy volunteers have received at least 1 dose of elsubrutinib; the most common side effect reported was headache, mild in severity.

As of 06 May 2020, from the Phase 2 RA and SLE studies, there are no identified safety risks for elsubrutinib or for ABBV-599 (elsubrutinib/upadacitinib) combination.

A detailed description of the preclinical pharmacology, metabolism, and toxicology datasets can be found in the elsubrutinib⁹ and upadacitinib⁸ Investigator's Brochures. The results of genetic toxicology testing indicate that elsubrutinib and upadacitinib are not genotoxic. Preclinical embryofetal development studies indicate that elsubrutinib and/or upadacitinib are embryotoxic, fetotoxic, and/or teratogenic.

Systemic lupus erythematosus patients are known to have an increased risk of thrombosis. Based on this and the potential risk of thrombosis with the use of JAK inhibitors, the use of estrogen-containing

contraceptives may further increase the risk of thrombotic events; therefore, the choice of contraceptive should be carefully considered.

In LTE Study M20-186, benefit/risk assessment of treatment groups for rollover may require subjects to be reassigned or discontinued based on the outcome of the unblinded interim analysis from the feeder Study M19-130 (See Section 4 Investigational Plan). Routine safety evaluations of all treatment groups will be performed. These include assessments of deaths, serious adverse events (SAEs), non-serious adverse events (AEs), withdrawals, and pregnancies, as well as routine monitoring by physical examinations, vital sign measurements, electrocardiograms, (ECGs), and clinical laboratory testing (hematology, chemistry, and urinalysis).

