5 STUDY ACTIVITIES

5.1 Eligibility Criteria

Subjects must meet all of the following criteria in order to be included in the study. Anything other than a positive response to the questions below will result in exclusion from study participation.

Consent

- 2 1. Subjects or their legally authorized representative (if required per local regulations) must understand and personally, voluntarily sign and date an informed consent, approved by an independent ethics committee (IEC)/institutional review board (IRB), prior to the initiation of any study-specific procedures. In Japan, subjects under 20 years of age must voluntarily sign and date an informed consent, in addition to their parent or legal guardian. Legally authorized representation will not apply in the case of Germany and France, and protected persons such as minors, adults under guardianship, pregnant women, persons deprived of their liberty and persons incapable or unable to express their consent cannot be included in the study.
- 2. Subjects are willing and able to comply with procedures required in this protocol.

Demographic and Laboratory Assessments

3. Subjects have completed Study M19-130 on study drug and have not developed any laboratory or clinical discontinuation criteria as defined in that study.

Relevant Study M19-130 eligibility requirements applicable to LTE Study M20-186 are as follows:

- a. Must be on stable background treatment throughout the study with antimalarial(s), prednisone (or prednisone-equivalent) (\leq 20 mg), azathioprine (\leq 150 mg), mycophenolate (\leq 2 g), leflunomide (\leq 20 mg), cyclosporine, tacrolimus, and/or MTX (\leq 20 mg).
 - The combination of background treatment with antimalarial(s) and/or prednisone (or equivalent) is permitted
 - and a single, but not multiple, additional immunosuppressant from the list above, is permitted.
- b. Must not have any active, chronic, or recurrent viral or bacterial infection that, based on the investigator's clinical assessment, makes the subject an unsuitable candidate for the study.
- c. Must not have active TB.
- d. Must not have a history of any malignancy except for successfully treated NMSC or localized carcinoma in-situ (CIS) of the cervix.
- e. Must not currently have clinically significant (per investigator's judgment) drug or alcohol abuse.

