5.5 Withdrawal of Subjects and Discontinuation of Study

Subjects can request to be discontinued from participating in the study at any time for any reason including but not limited to disease progression or lack of response to treatment. The investigator may discontinue any subject's study treatment at any time for any reason, including but not limited to, disease progression, lack of response to treatment, safety concerns, or failure to comply with the protocol. See Section 6.2 for toxicity management criteria.

Subjects will be discontinued from study drug immediately if any of the following occur:

- Development or worsening of lupus manifestation requiring introduction of certain prohibited medications or dosages when continuation of the study drug would place the subject at risk, as determined by the AbbVie TA MD. Introduction of the following in addition to study drug will require discontinuation of study drug immediately:
 - Cyclophosphamide

- Belimumab
- Rituximab
- More than one of the following in combination: azathioprine, mycophenolate, leflunomide,
 MTX, cyclosporine, or tacrolimus
- Plasmapheresis
- High dose steroids (≥ 60 mg prednisone-equivalent oral or parenteral)
- IVIG
- Clinically significant abnormal laboratory results or AEs, which rule out continuation of the study drug, as determined by the investigator or the AbbVie TA MD.
- Serious infections (e.g., pneumonia, sepsis) which cannot be adequately controlled by anti-infective treatment or would put the subject at risk for continued participation in the trial, as determined by the investigator or the AbbVie TA MD.
- The investigator believes it is in the best interest of the subject.
- The subject decides to withdraw from study drug or the study, or the Sponsor decides to discontinue 1 or more treatment groups after the planned Study M19-130 Interim Analysis.
- Inclusion or exclusion criterion violation was noted after the subject started study drug, when continuation of the study drug would place the subject at risk as determined by the AbbVie TA MD.
- Subject develops an ECG change considered clinically significant and with reasonable possibility
 of relationship to study drug or a confirmed absolute QTcF value > 500 msec or confirmed
 increase of ≥ 60 msec from Study M19-130 Baseline.
 - Subject's QTcF increases from Baseline ≥ 60 msec, the investigator will evaluate, confirm the value, and treatment should be stopped.
- Subject develops active TB at any time during the study.

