- Subject with latent TB who is non-compliant with or refuses to initiate TB prophylaxis.
- The subject becomes pregnant while on study drug.
- Malignancy, except for localized NMSC or CIS of the cervix.
- Subject is significantly non-compliant with study procedures, including inconsistent study drug
 dosing, which would put the subject at risk for continued participation in the trial as determined
 by the investigator or the AbbVie TA MD.
- Subject develops a GI perforation.
- If a diagnosis of deep vein thrombosis, pulmonary embolus, or non-cardiac, non-neurologic arterial thrombosis is confirmed.
- Subject develops active neuropsychiatric SLE (excluding lupus headache) as defined by the CNS portion of SLEDAI-2K or BILAG.
- Subject develops Class IV lupus nephritis (confirmed by biopsy).

In order to minimize missing data for efficacy and safety assessments, subjects who prematurely discontinue study drug treatment should, if possible:

- Continue in the study without receiving study drug
- Have all procedures performed outlined in the PD visit, preferably within 2 weeks of study drug discontinuation
- Continue with their regular study visit schedule

All attempts must be made to determine the date of the last study drug dose and the primary reason for discontinuation of study drug or study participation. The information will be recorded on the appropriate electronic case report form (eCRF) page. However, these procedures should not interfere with the initiation of any new treatments or therapeutic modalities that the investigator feels are necessary to treat the subject's condition. Following discontinuation of study drug, the subject should be treated in accordance with the investigator's best clinical judgment.

For subjects to be considered lost to follow-up, reasonable attempts must be made to obtain information on the subject's final status. At a minimum, 2 telephone calls must be made and 1 certified letter must be sent and documented in the subject's source documentation.

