The following adverse events of special interest (AESI) will be routinely monitored during the study:

- Serious infections
- Opportunistic infections
- Herpes zoster
- Active TB
- Malignancy (all types)
- Adjudicated GI perforations
- Adjudicated cardiovascular events (e.g., MACE)
- Anemia
- Neutropenia
- Lymphopenia
- Renal dysfunction
- Hepatic disorders
- Adjudicated embolic and thrombotic events (non-cardiac, non-CNS) including venous thromboembolic events defined as pulmonary embolism and deep vein thrombosis.

Adverse Event Severity and Relationship to Study Drug

Investigators will rate the severity of each AE according to the National Cancer Institute (NCI) Common Terminology Criteria for Adverse Events (CTCAE) version 5, which can be accessed at: https://ctep.cancer.gov/protocoldevelopment/electronic_applications/docs/ctcae_v5_quick_reference_8.5x11.pdf.

If no specific grading criteria are provided for the reported event, then the event should be as follows:

- Mild (Grade 1): asymptomatic or mild symptoms; clinical or diagnostic observations only; intervention not indicated;
- Moderate (Grade 2): minimal, local or noninvasive intervention indicated; limiting
 age-appropriate instrumental activities of daily living (ADL) (instrumental ADL refer to preparing
 meals, shopping for groceries or clothes, using the telephone, managing money, etc.);
- Severe (Grade 3 5):
 - Grade 3: severe or medically significant but not immediately life-threatening; hospitalization or prolongation of hospitalization indicated; disabling; limiting self-care ADL (self-care ADL refers to bathing, dressing and undressing, feeding self, using the toilet, taking medications, and not bedridden);

- Grade 4: Life-threatening consequences; urgent intervention indicated;
- Grade 5: Death related to AE.

The investigator will use the following definitions to assess the relationship of the AE to the use of study drug:

| Reasonable Possibility | After consideration of factors including timing of the event, biologic plausibility, clinical judgment, and potential alternative causes, there is sufficient evidence (information) to suggest a causal relationship. |
|------------------------------|--|
| No Reasonable Possibility | After consideration of factors including timing of the event, biologic plausibility, clinical judgment, and potential alternative causes, there is insufficient evidence (information) to suggest a causal relationship. |

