For causality assessments, events assessed as having a reasonable possibility of being related to the study drug will be considered "associated." Events assessed as having no reasonable possibility of being related to the study drug will be considered "not associated." In addition, when the investigator has not reported a causality or deemed it not assessable, AbbVie will consider the event associated.

If an investigator's opinion of no reasonable possibility of being related to study drug is given, an "Other" cause of event must be provided by the investigator for the SAE.

In Japan, the Principal Investigator will provide documentation of all SAEs to the Director of the investigative site and to the Sponsor.

Cardiovascular Adjudication Committee

An independent CAC will adjudicate all blinded cardiovascular and cerebrovascular events, embolic/thrombotic events, and deaths, as defined in the CAC charter.

Pregnancy

While not an AE, pregnancy in a study subject must be reported to AbbVie within 24 hours after the site becomes aware of the pregnancy. Subjects who become pregnant during the study must be discontinued from the study drug (Section 5.5). If a pregnancy occurs in a study subject or in the partner of a study subject, information regarding the pregnancy and the outcome will be collected.

In the event of pregnancy occurring in a subject's partner during the study, written informed consent from the partner must be obtained prior to collection of any such information. AbbVie will provide a separate consent form for this purpose. Pregnancy in a subject's partner will be collected from the date of the first dose in LTE Study M20-186 through 30 days following the last dose of study drug.

The pregnancy outcome of an elective or spontaneous abortion, stillbirth, or congenital anomaly is considered an SAE and must be reported to AbbVie within 24 hours after the site becomes aware of the event.

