Subjects should be closely monitored for the development of signs and symptoms of infection during and after treatment with study drug. Study drug should be interrupted if a subject develops a serious infection (including COVID-19) or a serious opportunistic infection (excludes non-serious oropharyngeal candidiasis). A subject who develops a new infection during treatment with study drug should undergo prompt diagnostic testing appropriate for an immunocompromised subject. As appropriate, antimicrobial therapy should be initiated, and the subject should be closely monitored. Study drug may be restarted once the infection has been successfully treated. Subjects who develop active TB must be discontinued from the study drug.

Canada only: Investigators should be advised to follow local public health guidelines in order to prevent subjects enrolled in these trials from acquiring TB.

COVID-19: Interrupt study drug in subjects with a confirmed diagnosis of COVID-19. Consider interrupting study drug in subjects with signs and/or symptoms and suspicion of COVID-19. The appropriate COVID-19 eCRFs should be completed. If a subject has a confirmed or suspected COVID-19 infection and study drug was interrupted, the investigator should contact the AbbVie TA MD before reintroducing study drug.

Management of Herpes Zoster

If a subject develops herpes zoster, the investigator should consider temporarily interrupting study drug until the episode resolves.

Management of Serious Gastrointestinal Events

Subjects presenting with the onset of signs or symptoms of a serious GI event should be evaluated promptly for early diagnosis and treatment. If the diagnosis of GI perforation is confirmed, the subject must be discontinued from the study drug.

Management of Cardiovascular Events

Subjects presenting with potential cardiovascular events should be appropriately assessed and carefully monitored. These events will be reviewed and adjudicated by an independent CAC in a blinded manner.

Management of Malignancy

Subjects who develop malignancy other than NMSC or CIS of the cervix must be discontinued from the study drug. Information including histopathological results should be queried for the confirmation of the diagnosis. Periodic skin examination is recommended for subjects who are at increased risk for skin cancer.

Management of ECG Abnormality

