Appendix B. Definition of Adverse Events of Special Interest

Adverse Events of Special Interest (AESI) will be identified using the following search criteria:

AESI	Type of MedDRA Query	Broad or Narrow Search	SMQ/CMQ Search Criteria
Serious Infections	CMQ		"Infections" – Subset for SAEs
Opportunistic Infection excluding Tuberculosis and Herpes Zoster	CMQ		"Opportunistic Infection" excluding Tuberculosis and Herpes Zoster CMQ
Herpes Zoster	CMQ		"Herpes Zoster"
Active Tuberculosis	CMQ		"Active Tuberculosis"
Possible Malignancy	SMQ	Narrow	"Malignancies"
Malignancy	SMQ	Narrow	"Malignant Tumours"
Malignancies excluding NMSC	SMQ	Narrow	"Malignant Tumours" removing NMSC output
Non-Melanoma Skin Cancer (NMSC)	SMQ	Narrow	"Skin Malignant Tumours" removing Melanoma CMQ
Adjudicated GI perforations			Based on adjudicated results (the identification of events to be adjudicated are described in the GI Perforation charter)
Adjudicated cardiovascular events: MACE*		Output from CAC	
Cardiovascular Death			
Non-fatal Myocardial Infarction			
Non-fatal Stroke			
Undetermined/Unknown Cause of Deaths			
Other Cardiovascular events			
Anemia	CMQ		"Non-Hemolytic and Non-Aplastic Anemias"
Neutropenia	CMQ		"Hematological Toxicity – Neutropenia"
Lymphopenia	CMQ		"Hematological Toxicity - Lymphopenia"

AESI	Type of MedDRA Query	Broad or Narrow Search	SMQ/CMQ Search Criteria
Renal dysfunction	SMQ	Narrow	"Acute Renal Failure"
Hepatic disorders	SMQ	Narrow	"Drug Related Hepatic Disorders"
Adjudicated Thrombotic Events: VTE**	Output from CAC		
Deep Vein Thrombosis			
Pulmonary Embolism			
Other Venous Thrombosis			

* MACE: Major Adverse Cardiovascular Events, defined as cardiovascular death, non-fatal myocardial infarction and non-fatal stroke.

** VTE: Venous thromboembolic events, defined as deep vein thrombosis (DVT) and pulmonary embolism (PE) (fatal and non-fatal).

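### Protocol Section 6.2 exempts all non-melanoma skin cancer from the malignancy stop, while Section 5.5 exempts only localized disease

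*Protocol*

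**What the plan says.** Protocol Section 5.5 opens its list of stopping events with "Subjects will be discontinued from study drug immediately if any of the following occur". One entry is "Malignancy, except for localized NMSC or CIS of the cervix". The same section refers the reader to Section 6.2 for toxicity management criteria.

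Protocol Section 6.2, under the management of malignancy, says "Subjects who develop malignancy other than NMSC or CIS of the cervix must be discontinued from the study drug". It then asks that histopathology be queried to confirm the diagnosis and recommends periodic skin examination for subjects at increased risk of skin cancer. It does not refer back to Section 5.5.

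The SAP contains no malignancy stopping rule. Its Appendix B defines the malignancy events of special interest, including separate categories for NMSC and for malignancies excluding NMSC. Its Appendix A counts, as a protocol deviation, subjects who met withdrawal criteria but were not withdrawn.

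**The concern.** Both sections set a mandatory stop for the same event, but the exemption is wider in Section 6.2. Section 5.5 spares only localized NMSC; Section 6.2 spares NMSC of any extent.

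Section 2.2 names NMSC among the potential risks of upadacitinib, which is given in three of the four treatment regimens. Section 6.2 is where a site would look when managing an event. A site that relied on its malignancy paragraph alone could keep a subject with locally advanced or metastatic NMSC on study drug when Section 5.5 requires an immediate stop. A reader using Section 6.2 alone would also not recognise that subject as a deviation under SAP Appendix A.

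**Working it through.** No arithmetic applies. The check sets the two current rules side by side and works through the cases.

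| Event on treatment | Section 5.5 | Section 6.2, malignancy paragraph | Agree? |
|---|---|---|---|
| Localized NMSC | No stop required | No stop required | Yes |
| CIS of the cervix | No stop required | No stop required | Yes |
| Any other malignancy that is not NMSC | Stop | Stop | Yes |
| NMSC that is not localized | Stop, immediately | No stop required | **No** |

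The rules differ in the last row only. Three further steps test whether other text in the protocol removes the difference.

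1. **Cross-references.** Section 5.5 points to Section 6.2. Section 6.2 does not point back, and neither states precedence, so the link leads from the stricter wording to the looser one. By contrast, the pregnancy paragraph in Section 6.1 does cite Section 5.5 for its stop.

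2. **The general Grade 3 and Grade 4 rule in Section 6.2.** This rule covers adverse events other than those given specific management. Malignancies are on Section 6.2's list of specifically managed events, so on its wording the general rule does not reach them. Even if it did, it depends on the investigator judging the event to be possibly related to study drug, and at Grade 3 it calls for interruption, not discontinuation.

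3. **How other stops are restated.** Active tuberculosis, gastrointestinal perforation, confirmed thrombosis and biopsy-confirmed Class IV lupus nephritis are stops in Section 5.5, and Section 6.2 (including Table 4) repeats each with the same scope. This suggests that the missing qualifier for NMSC is an oversight and not a deliberate relaxation.

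The entry criterion in Section 5.1 (item 3d) reads "Must not have a history of any malignancy except for successfully treated NMSC or localized carcinoma in-situ (CIS) of the cervix". It concerns history at entry and uses a different qualifier for NMSC, so it is background only. The finding rests on Sections 5.5 and 6.2.

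On the analysis side, SAP Appendix B identifies NMSC by MedDRA query and not by extent of disease. Tabulations of events of special interest are therefore defined in the same way under either wording.

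**The case against.** The strongest reply is that the two texts do not contradict each other. Each says when study drug must stop. Section 6.2 never says that a subject with NMSC may continue; it only imposes no stop of its own. A site that follows Section 5.5 complies with both, so Section 6.2 is an incomplete restatement of a rule that is fully stated elsewhere. This is correct and is the main reason the point is minor.

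The reply continues that harm requires a site to overlook the protocol's discontinuation section, and that several other controls would have to fail as well:

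- Malignancy of all types is monitored as an event of special interest (Section 6.1).
- Histopathology is queried (Section 6.2).
- The data monitoring committee reviews unblinded safety data (Section 6.3).
- Section 5.5 separately requires a stop for clinically significant adverse events that rule out continuation, as determined by the investigator or the sponsor's medical director, and whenever the investigator believes stopping is in the subject's best interest.

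These controls are real and make unnoticed continuation unlikely.

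It can also be said that the missing back-reference is a matter of house style, since Section 6.2 restates other stops without citing Section 5.5. That is fair, and the absent citation is not a defect by itself. It matters here only because the restated wording differs from the original, which is not so for the stops compared above.

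What remains is that Section 6.2, read alone, gives the wrong result in one case, and nothing in the protocol tells the reader which wording takes priority.

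**Conclusion.** The concern holds, at low severity. The two stopping rules differ for NMSC that is not localized and agree in every other case. Section 5.5 still applies, so this is a loose restatement of a safety rule and not a reversed one.

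The size of the problem rests on one assumption: non-localized NMSC will be rare in this population. The documents give no frequency. The inconsistency does not depend on any rate, although its practical weight does. No endpoint, analysis set or planned efficacy or adverse-event summary depends on the wording. The only reporting item that could be touched is the deviation count in SAP Appendix A, and then only for a subject with non-localized NMSC who was kept on study drug.

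**What to change.** In Section 6.2, insert the word *localized* before NMSC so that the exemption matches Section 5.5. Alternatively, cite Section 5.5 in that sentence as the governing criterion, as the pregnancy paragraph in Section 6.1 already does. Inserting the word is preferable, because Section 6.2 then gives the right answer when read alone.

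The cost is one word or one cross-reference. It can be included in the next amendment and does not justify an amendment by itself. The SAP needs no change.
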